## 1 PROTOCOL SUMMARY

### 1.1 SYNOPSIS

|   |  |
|---|--|
| Title:                             | An Interactive Web Platform to Teach Children Hunting, Shooting and Firearms Safety  |
| Study Background:                  | 
Firearms injuries are a significant pediatric public health challenge in the United States. The Centers for Disease Control (CDC) estimates 803 children ages 0-15 were killed by firearms in the United States in 2018, and an additional 2,422 children visited emergency rooms for treatment after a firearms injury. Roughly half of children who are hospitalized for a firearm-related injury leave the hospital with a disability, creating long-term health, medical system, financial, family, and societal burden.
 
About one-third of firearms injuries to children under age 15 are due to unintentional causes rather than suicide or homicide. Those injuries tally over 80 child deaths and 1200 serious injuries every year in the United States and represent the current focus.
 
The present study implements a randomized clinical trial to evaluate ShootSafe, an interactive, engaging, educational website to teach children firearms safety.
 |
| Objectives:                        | The research will evaluate whether ShootSafe achieves 3 goals: (a) teach children ages 10-12 basic knowledge and skills needed to hunt, shoot, and use firearms safely; (b) help children learn and hone critical cognitive skills of impulse control and hypothetical thinking needed to use firearms safely; and (c) alter children's perceptions about their own vulnerability and susceptibility to firearms-related injuries, the severity of those injuries, and their perceived norms about peer behavior surrounding firearms use.   |
| Study Population:                  | Children ages 10-12 years who have exposure to firearms  |
| Phase:                             | I-II   |
| Description of Study Intervention: | Interactive, engaging, and educational website   |

## 2 INTRODUCTION

### 2.1 STUDY RATIONALE

Firearms injuries are a significant pediatric public health challenge in the United States. The Centers for Disease Control (CDC) estimates 803 children ages 0-15 were killed by firearms in the United States in 2018, and an additional 2,422 children visited emergency rooms for treatment after a firearms injury. Roughly half of children who are hospitalized for a firearm-related injury leave the hospital with a disability, creating long-term health, medical system, financial, family, and societal burden.

About one-third of firearms injuries to children under age 15 are due to unintentional causes rather than suicide or homicide. Those injuries tally over 80 child deaths and 1200 serious injuries every year in the United States and represent the current focus.

The present study implements a randomized clinical trial to evaluate ShootSafe, an interactive, engaging, educational website to teach children firearms safety.

### 2.2 BACKGROUND

#### Children and Firearms

American children are routinely exposed to firearms in their homes. A study of 314 parent-child dyads seeking treatment at a rural health clinic in Alabama found that 201 of the homes (64%) had firearms present in their home. Among those 201, 73% of children ages 5-10 and 79% of children ages 10-14 knew where the guns were stored. An equal number of children – 36% – in both age groups reported they had handled the firearms, including 52% of boys. Our laboratory's research with 1561 fifth-graders in the Birmingham metropolitan area found that 31% of families reported having firearms in the home, with higher rates among families with Non-Hispanic White children than those with African-American or Hispanic children. Just under half of the 440 families in that study with firearms in their homes (47%) stated they used the firearms for hunting.

Recognizing the methodological limitations of self-report data concerning firearms ownership and usage, a different study by our research team used home inspections to evaluate risk to Birmingham children. In a study of 42 Birmingham-area families who agreed to have their homes inspected for broad child safety risks (mean child age = 15 years), 38% had a firearm present and 29% had a firearm present and unlocked. Among the 23% of families with rifles present, 79% stored the rifle unlocked, 61% stored ammunition in the same place as the rifle, and 15% stored the rifle unlocked and loaded with ammunition.

Online forums suggest children as young as age 5 and 6 sometimes start hunting and shooting with their parents. Most United States state laws permit children of any age to hunt legally under supervision by an adult. In many states, children can legally hunt unsupervised by an adult at any age if they complete a hunter education training program; the remaining states usually limit unsupervised hunting to children over age 10 or 12 years. Anecdotal reports widely cite the fact that children typically begin shooting and hunting during the elementary school years and often hunt and shoot alone or with peers and siblings by age 10 or 12, whether legal in their state or not.

#### Firearms Injuries while Hunting and Shooting

Among adults, between 25-33% of unintentional firearms injuries occur while hunting. In one case series of serious hunting injuries over a 2-year period, 10 of the 68 (15%) shooters were under age

15 and an additional 12 shooters (18%) were between the ages of 15-17. Half of the 22 children who unintentionally shot a person while hunting were being supervised by an adult while hunting, and half were not. 28% of the cases in the series were fatal.

Data on injuries and fatalities related to recreational shooting are less readily available, but one report suggests about 3% of unintentional firearms fatalities from 2003-2006 in selected US states were known to be the direct result of an incident during target shooting activities. An additional 21% occurred during hunting, 11% while cleaning or loading the firearm, and 5% while carrying or handling it. A large portion (15%) were due to other or unknown causes and may also have been associated with hunting or shooting.

### **Previous Research on Firearms Safety Programs for Children**

A large portion of existing child firearms safety programs focus on changing adult behavior through strategies such as safe firearms storage rather than on changing children's behavior with firearms. Two recent systematic reviews, which identified 12 and 10 studies respectively targeting children (and 9 others targeting adolescents in the Ngo et al. review), suggest most existing programs to teach children firearms safety are ineffective. A surprising number of published empirical trials yield either null results or results that document capacity to teach children basic knowledge but not translate that knowledge into safer behavior.

Despite the discouraging results of previous research, a smattering of studies offer promising results to guide the current study. Perhaps most influential is a series of studies by Miltenberger and colleagues that test the use of active learning strategies, generally delivered in small-group or classroom settings, to teach children firearms safety. In all cases, these studies use small sample sizes (largest N = 45 and many Ns < 10). The findings generally suggest children exposed to theory-based active-learning activities involving behavioral strategies like modeling, rehearsal and feedback successfully learn both relevant firearms safety skills as well as displaying appropriate behavior in role-play scenarios following the training. We adopt these active-learning behavioral strategies into an internet-based delivery system for ShootSafe.

## **2.3 RISK/BENEFIT ASSESSMENT**

### **2.3.1 KNOWN POTENTIAL RISKS**

Psychological risks include slight possibility that children may believe they are more safe using firearms after participating in the study (iatrogenic effects) and slight risk that children might become more excited about shooting, hunting, and using firearms after participating in the study, increasing risk of injury through exposure.

There is minimal social risk from participating in this study. The primary risk results from the possibility for a breach of confidentiality. No data we collect will be highly personal, but we will collect information that participants may wish to keep private (such as household income).

There are no known physical, economic, or legal risks involved in study participation.

### **2.3.2 KNOWN POTENTIAL BENEFITS**

Study results may provide valuable information to society concerning ways to reduce risk of firearms injuries to children. Study participants may learn about firearms safety (intervention group) or nutrition (control group).

### 3 STUDY DESIGN

#### 3.1 OVERALL DESIGN

A randomized controlled trial with two arms will be conducted.

### 4 STUDY POPULATION

#### 4.1 INCLUSION CRITERIA

- Child ages 10-12
- Live within driving distance of laboratory in Birmingham, Alabama
- Child has exposure to firearms through personal experience with firearms in the home or engagement in hunting or shooting activities

#### 4.2 EXCLUSION CRITERIA

- Inability to complete study protocol in English
- Physical or mental disability that prohibits valid participation in the study

### 5 STUDY INTERVENTION

#### 5.1 STUDY INTERVENTION(S) ADMINISTRATION

##### 5.1.1 STUDY INTERVENTION DESCRIPTION

All intervention activities will occur in a laboratory setting where we can monitor usage and control exposure to the intervention. Children in both intervention groups will use the randomly-assigned websites during two 45-minute sessions.

The active ShootSafe intervention offers a wide range of stories, games and videos for children to experience in a sequential manner, such that children step through the website in a prescribed order. The comparison group will visit nourishinteractive.com, a website that provides educational games and activities relevant to child nutrition and exercise. Of similar size/scope to ShootSafe, nourishinteractive.com offers extensive games, stories, and interactive activities for children in a range of age groups, including our target age. Children in the comparison group will self-direct to their preferred activities on the website.

#### 5.2 MEASURES TO MINIMIZE BIAS: RANDOMIZATION

Randomization to condition will be achieved using a 1:1 allocation ratio. The research team will determine randomized assignment through a random number generator and randomized order list concealed to all parties prior to assignment. Children will be assigned to a condition upon arrival to the first training visit, following all baseline data collection.

## 6 STUDY INTERVENTION DISCONTINUATION AND PARTICIPANT DISCONTINUATION/WITHDRAWAL

### 6.1 DISCONTINUATION OF STUDY INTERVENTION

The intervention will be discontinued if participants request it or if there is any sign of adverse or iatrogenic effect.

### 6.2 PARTICIPANT DISCONTINUATION/WITHDRAWAL FROM THE STUDY

Participants are free to withdraw from participation in the study at any time upon request. An investigator may discontinue or withdraw a participant from the study for the following reasons:

- Non-compliance to study protocol
- If any clinical adverse event (AE), laboratory abnormality, or other medical condition or situation occurs such that continued participation in the study would not be in the best interest of the participant

### 6.3 LOST TO FOLLOW-UP

A participant will be considered lost to follow-up if they fail to attend scheduled visits and/or are unable to be contacted by the study site staff.

## 7 STUDY ASSESSMENTS AND PROCEDURES

### 7.1 STUDY ASSESSMENTS

The primary study outcome will be children's behavior with firearms, as assessed through three strategies: (a) a basic written "quiz" concerning firearms safety; (b) a series of photographs showing various safe and unsafe situations, in which children respond whether the situation is safe or not; and a role-play simulation.

In the role play simulation, we will arrange replicated hunting and shooting scenes in the laboratory and children will use toy firearms to engage in simulated hunting and shooting activities. They also will prepare for outings (e.g., select proper attire) and return to a different room to "store" their firearms safely. All behavior will be videotaped and subsequently coded for risk-taking using an objective coding scheme.

Several secondary measures will be assessed also.

### 7.2 ADVERSE EVENTS AND SERIOUS ADVERSE EVENTS

### 7.2.1 DEFINITION OF ADVERSE EVENTS (AE)

Adverse event means any untoward medical occurrence associated with the use of an intervention in humans, whether or not considered intervention-related (21 CFR 312.32 (a)).

### 7.2.2 DEFINITION OF SERIOUS ADVERSE EVENTS (SAE)

An adverse event (AE) is considered “serious” if, in the view of either the investigator or sponsor, it results in any of the following outcomes:

- Death
- A life-threatening adverse event (of note, the term “life-threatening” refers to an event in which the participant was at risk of death at the time of the event, rather than to an event which hypothetically might have caused death if it were more severe)
- inpatient hospitalization or prolongation of existing hospitalization
- a persistent or significant incapacity or substantial disruption of the ability to conduct normal life functions
- or a congenital anomaly/birth defect.

Important medical events that may not result in death, be life-threatening, or require hospitalization may be considered serious when, based upon appropriate medical judgment, they may jeopardize the participant and may require medical or surgical intervention to prevent one of the outcomes listed in this definition. Examples of such medical events include allergic bronchospasm requiring intensive treatment in an emergency room or at home, blood dyscrasias or convulsions that do not result in inpatient hospitalization, or the development of drug dependency or drug abuse.

### 7.2.3 CLASSIFICATION OF AN ADVERSE EVENT

#### 7.2.3.1 SEVERITY OF EVENT

For adverse events (AEs), the following guidelines will be used to describe severity:

- **Mild** – Events require minimal or no treatment and do not interfere with the participant’s daily activities.
- **Moderate** – Events result in a low level of inconvenience or concern with the therapeutic measures. Moderate events may cause some interference with functioning.
- **Severe** – Events interrupt a participant’s usual daily activity and may require systemic drug therapy or other treatment. Severe events are usually potentially life-threatening or incapacitating. Of note, the term “severe” does not necessarily equate to “serious.”

#### 7.2.3.2 RELATIONSHIP TO STUDY INTERVENTION

All adverse events (AEs) must have their relationship to study intervention assessed by the researchers who examine and evaluate the participant based on temporal relationship and his/her clinical judgment. The degree of certainty about causality will be graded using the categories below. In a clinical trial, the study product must always be suspect.

- **Related** – The AE is known to occur with the study intervention, there is a reasonable possibility that the study intervention caused the AE, or there is a temporal relationship between the study

intervention and event. Reasonable possibility means that there is evidence to suggest a causal relationship between the study intervention and the AE.

- **Not Related** – There is not a reasonable possibility that the administration of the study intervention caused the event, there is no temporal relationship between the study intervention and event onset, or an alternate etiology has been established.

#### 7.2.3.3 EXPECTEDNESS

The Principal Investigator will be responsible for determining whether an adverse event (AE) is expected or unexpected. An AE will be considered unexpected if the nature, severity, or frequency of the event is not consistent with the risk information previously described for the study intervention.

#### 7.2.4 TIME PERIOD AND FREQUENCY FOR EVENT ASSESSMENT AND FOLLOW-UP

The occurrence of an adverse event (AE) or serious adverse event (SAE) may come to the attention of study personnel during study visits and interviews of a study participant, or upon review by a study monitor.

All AEs including local and systemic reactions not meeting the criteria for SAEs will be captured on the appropriate case report form (CRF). Information to be collected includes event description, time of onset, assessment of severity, relationship to study activities, and time of resolution/stabilization of the event. All AEs occurring while on study will be documented appropriately regardless of relationship. All AEs will be followed to adequate resolution.

#### 7.2.5 ADVERSE AND SERIOUS ADVERSE EVENT REPORTING

All serious adverse events will be reported to the IRB according to regulatory requirements. The Principal Investigator will report to the sponsor any serious adverse event in a timely manner. All serious adverse events (SAEs) will be followed until satisfactory resolution.

### 7.3 UNANTICIPATED PROBLEMS

#### 7.3.1 DEFINITION OF UNANTICIPATED PROBLEMS (UP)

The Office for Human Research Protections (OHRP) considers unanticipated problems involving risks to participants or others to include, in general, any incident, experience, or outcome that meets all of the following criteria:

- Unexpected in terms of nature, severity, or frequency given (a) the research procedures that are described in the protocol-related documents, such as the Institutional Review Board (IRB)-approved research protocol and informed consent document; and (b) the characteristics of the participant population being studied;
- Related or possibly related to participation in the research (“possibly related” means there is a reasonable possibility that the incident, experience, or outcome may have been caused by the procedures involved in the research); and
- Suggests that the research places participants or others at a greater risk of harm (including physical, psychological, economic, or social harm) than was previously known or recognized.

#### 7.3.2 UNANTICIPATED PROBLEM REPORTING

The investigator will report unanticipated problems (UPs) to the reviewing Institutional Review Board (IRB). The UP report will include the following information:

- Protocol identifying information: protocol title and number, PI's name, and the IRB project number;
- A detailed description of the event, incident, experience, or outcome;
- An explanation of the basis for determining that the event, incident, experience, or outcome represents an UP;
- A description of any changes to the protocol or other corrective actions that have been taken or are proposed in response to the UP.

To satisfy the requirement for prompt reporting, UPs will be reported using the following timeline:

- UPs that are serious adverse events (SAEs) will be reported to the IRB within 10 working days of the investigator becoming aware of the event.
- Any other UP will be reported to the IRB within 10 working days of the investigator becoming aware of the problem.

## 8 STATISTICAL CONSIDERATIONS

### 8.1 STATISTICAL HYPOTHESES

Primary Endpoints: scores from the quiz, photograph, and role play simulation tasks

### 8.2 SAMPLE SIZE DETERMINATION

A power analysis was conducted to determine sample size using PASS 14 (Power Analysis and Sample Size) software. Based on previous work, we conservatively assumed change of 3 (SD = 2) in the ShootSafe website condition and 2 (SD = 2) in the comparison condition, yielding an anticipated medium effect size of 0.5. That is, we powered to detect a difference of 0.5 standard deviations between the ShootSafe website and control condition groups. Using 2 tails and  $\alpha = .05$  and assuming an independent samples t-test is conducted, a sample size of 70 per group provides 90% power to detect an effect size as small as 0.5. With the same assumptions and retaining  $n = 70$  per group, we estimate 95% power to detect an effect size of at least 0.56. As we are using a linear mixed model to assess the specific aims rather than a t-test, we will ensure that power is higher yet than that determined above since we will incorporate the observed correlation between the trials. Conservatively inflating 15% to account for attrition, we propose a sample size of 162, which is amply large to test our hypotheses.

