### 8.3 STATISTICAL ANALYSES

Data analysis will be conducted with condition masked. Descriptive analyses will be conducted first to examine the distributions of key variables and identify any unusual cases or outliers. Most outcome variables are expected to be normally distributed, but variables with substantially skewed distributions will be appropriately transformed so that linear models may be applied without violating assumptions.

Following inspection and interpretation of descriptive statistics, primary inferential data analyses will address the study's specific aims. Primary analyses will be conducted with the full sample using an intention-to-treat analytic approach.

The primary aim is to evaluate whether the website improves children's safety with firearms. This aim will be measured through scores from the quiz, photograph, and role play simulation tasks. We will standardize each outcome variable and evaluate through correlation matrices and factor analysis to determine if they appear to be measuring the same underlying construct. If so, they will be aggregated. Otherwise, they will be assessed as independent outcome variables.

Linear mixed models will evaluate our primary hypotheses. Linear mixed models were selected primarily because they offer the ability to allow for correlation within each child based on all three of the child's measurements. Group differences will be tested by fitting the following model:

$$E[Y_{ij} | X, Z] = \beta_0 + \beta_1 X_{\text{group}} + \beta_2 X_{\text{time}} + \beta_3 X_{\text{group}} * X_{\text{time}}$$

where time will be entered into the model as a categorical variable (baseline vs post vs follow-up) utilizing effect cell coding so that we can determine whether changes in the outcomes between different time points differ by intervention group. Of greatest interest will be  $\beta_3$ , as this parameter will tell us whether the effect of the intervention group differs between baseline, post-intervention and follow-up time points. If we find that  $\beta_3$  is significant, we will perform orthogonal contrasts to determine which specific time points differ from each other. To increase statistical efficiency, we will use previous literature to identify covariates that may be highly associated with the outcome before statistical analysis, and those covariates will be included in the linear model.

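### Section 8.2 gives power for a 1-df t-test on one change score, not for the 2-df group-by-time test in 8.3, so the further gain it claims for the mixed model is not ensured

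*Combined protocol and SAP*

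**What the plan says.** Section 8.2 (Sample Size Determination) assumes a "change of 3 (SD = 2) in the ShootSafe website condition and 2 (SD = 2) in the comparison condition", which it treats as an effect size of 0.5. The calculation, two-tailed at alpha .05, is put this way: "assuming an independent samples t-test is conducted, a sample size of 70 per group provides 90% power to detect an effect size as small as" that same value. It also gives 95% power at an effect size of 0.56. On the move from t-test to mixed model it says that "we will ensure that power is higher yet than that determined above since we will incorporate the observed correlation between the trials". No calculation supports that sentence. After an allowance for attrition, 162 children are to be enrolled.

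Section 8.3 (Statistical Analyses) fits group, time and group-by-time terms, where "time will be entered into the model as a categorical variable (baseline vs post vs follow-up"). The interaction is named as the term of greatest interest, because "this parameter will tell us whether the effect of the intervention group differs between baseline, post-intervention and follow-up time points". Contrasts between particular visits are made only if the interaction is significant.

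**The concern.** The test that was sized and the test that decides the primary aim are not the same. Two groups by three categorical visits give two interaction parameters, tested jointly before any contrast. A t-test on one change score has one degree of freedom and uses nothing from the third visit.

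The reason given for expecting more power is the correlation within a child. The SD of 2 is attached to the change, so on its natural reading the baseline-to-post correlation has already been counted. What remains is the information from the follow-up visit, and it comes with a second degree of freedom. Whether the net effect is a gain or a loss depends on how much of the effect persists and how the visits correlate. At stake is whether the stated power, and the false-negative risk that it implies, belongs to the primary analysis.

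**Working it through.** **Inputs from section 8.2:** difference in change 3 − 2 = 1; SD of change 2; d = 1/2 = 0.5; n = 70 per group; alpha .05, two-tailed.

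**Assumptions, because the documents give no values:** the share f of the post effect kept at follow-up, and the correlation r between the two change scores (post − baseline and follow-up − baseline). Both change scores are given SD 2. Equally correlated visits imply r = 0.5.

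**Step 1: the plan's own figure.** For the t-test, the noncentrality is d × √(n/2) = 0.5 × √35 = 2.96 on 138 df.
- Two-sided .05: 83.6%.
- One-sided .05: 90.3%.
- At d = 0.56: 90.8% two-sided, 95.1% one-sided.

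Both printed figures (90% and 95%) match a one-sided test, not the two tails stated. That is a separate error, so the right benchmark below is 83.6%.

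**Step 2: the 2-df interaction test.** With group differences (1, f) in the two change scores and covariance matrix Σ (variances 4, correlation r), the noncentrality is

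λ = (n/2) × δ′Σ⁻¹δ = 35 × (1 − 2rf + f²) / [4(1 − r²)],

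referred to a noncentral F on (2, 137) df.

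At r = 0.5:

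| Share kept at follow-up | λ | Power |
|---|---|---|
| 100% | 11.67 | 86.6% |
| 75% | 9.48 | 78.4% |
| 50% | 8.75 | 74.8% |
| 25% | 9.48 | 78.4% |
| 0% | 11.67 | 86.6% |

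With 276 denominator df, as in a pooled repeated-measures analysis, the figures at 50% and 100% kept are 75.3% and 87.0%. The choice of df moves power by about half a point.

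**Step 3: why about 75% is a floor.** For a fixed post effect, λ is smallest at f = r, where it equals 35 × 1/4 = 8.75. The square of the t-test noncentrality is also 0.25 × 35 = 8.75. At that point follow-up adds no signal, and the second degree of freedom alone takes power from 83.6% to 74.8%. At any other f the third visit recovers some or all of that loss.

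**Step 4: sensitivity.**

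| r | 0% kept | 25% | 50% | 75% | 100% |
|---|---|---|---|---|---|
| 0.3 | 79.0% | 75.0% | 76.8% | 83.4% | 91.2% |
| 0.7 | 96.5% | 88.2% | 78.2% | 75.1% | 81.8% |

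If all 162 children complete (81 per group), r = 0.5 gives 81.3% at half kept and 91.3% if fully kept or fully lost. The two-sided t-test at 81 per group gives 88.5%.

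**The case against.** The strongest objection is that the 2-df test is not uniformly weaker. Under equally correlated visits, an effect fully kept or fully lost gives 86.6%, above the correct t-test figure. Some settings pass 90%: 91.2% at r = 0.3 with the effect kept, and 96.5% at r = 0.7 with it lost. An effect that grew to 125% by follow-up would give 94.4% at r = 0.5. Section 8.3 also retains partial data and plans prognostic covariates, both of which could help, and 70 per group is the number after attrition. All of this stands. It shows that a gain is possible, not that it is ensured.

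One could also say that section 8.3 prints a single β₃. But time is explicitly a three-level category, and contrasts follow only from a significant interaction, so a joint 2-df test is the natural reading.

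A reader might go further and infer that true power is 75% against a stated 90%, a 15-point loss with a false-negative risk of 25% rather than 10%. The documents do not support that. About 6 of those 15 points (90 − 83.6) come from the sidedness error. The 75% is the minimum over follow-up effects, not the value for every partial fade. The fade itself is an assumption, because no follow-up effect is stated anywhere. Section 8.2 also does not say which of the three outcome measures the change of 3 versus 2 describes, and 8.3 may combine them, so no single figure can be called the power of the primary analysis.

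**Conclusion.** The point holds as a gap between the sizing and the primary test. Section 8.2 does not give the power of the interaction test, and its assurance of a further gain has no support in the documents. For 70 completers per group, change SD 2, d = 0.5 at post and equally correlated visits, the 2-df test has about 75% to 87% power. That runs from 8.8 points below to 3.0 points above the correct two-sided t-test figure of 83.6%. Over change-score correlations of 0.3 to 0.7 the range is about 75% to 96%. With all 81 per group complete and equally correlated visits it is about 81% to 91%. The ranges cover 0% to 100% of the post effect kept at follow-up and take no credit for covariates. They do not show that the trial is too small; they show that its power for the primary test has not been established.

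**What to change.** In section 8.2:

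1. Delete the sentence claiming that the mixed model's power will exceed the t-test figure.
2. Correct the two-sided t-test power at d = 0.5 to about 84%. The figure at 0.56 needs the same correction, from 95% to about 91%.
3. State the power of the 2-df group-by-time test at two-sided .05 for named follow-up effects (for example 100%, 50% and 0% of the post effect kept) and named correlations between the change scores, all labelled as assumptions. Say which outcome the assumed change and SD refer to, and whether n is completers or all randomized.

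The cost is some rewording and a short calculation, with no more children. The downside is a less favourable stated power. The sponsor could instead name one 1-df contrast as primary so that a t-test calculation applies. That is an optional design choice, because a baseline-to-post contrast would take follow-up out of the primary inference, and it is not part of this correction.

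### Section 8.2 claims 90% and 95% power for a two-tailed t-test, but its own inputs give about 84% and 91%; the printed figures match a one-sided test at .05

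*Combined protocol and SAP*

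**What the plan says.** Everything needed is in section 8.2 (Sample Size Determination) of the combined protocol and SAP.

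- **Effect assumed:** "change of 3 (SD = 2) in the ShootSafe website condition and 2 (SD = 2) in the comparison condition". The section reads this as an effect size of 0.5: "we powered to detect a difference of 0.5 standard deviations between the ShootSafe website and control condition groups".
- **Test assumed:** the sentence giving the power opens "Using 2 tails and" sets alpha at .05, and continues "assuming an independent samples t-test is conducted".
- **First power figure:** "a sample size of 70 per group provides 90% power to detect an effect size as small as 0.5".
- **Second power figure**, on the same assumptions and the same 70 per group: "we estimate 95% power to detect an effect size of at least 0.56".
- **Total:** "Conservatively inflating 15% to account for attrition, we propose a sample size of 162". The section calls this total amply large.

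The section adds that the real analysis will be a linear mixed model and expects its power to exceed the t-test figure. It gives no correlation and no size for that gain. Section 5.2 sets 1:1 allocation. No one-sided test is mentioned anywhere in the document.

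**The concern.** For a two-sided t-test at .05, a standardised difference of 0.5 usually needs somewhat more than 80 per group for 90% power, so 70 looked too few. Both printed figures are higher than expected, which points to a setting in the calculation rather than a rounding slip.

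The power statement is the only quantified support for enrolling 162 children. If it is overstated, the risk of missing the target effect is larger than the plan admits. A reader who later meets a non-significant result would also weigh it as coming from a trial with 90% power.

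**Working it through.** **Inputs (section 8.2; allocation from section 5.2).** Mean change 3 against 2, SD 2 in each arm, so d = (3 − 2)/2 = 0.5. n = 70 per group, 1:1. Alpha .05, two-tailed, independent-samples t-test.

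**Formula.** Exact power comes from the noncentral t distribution with df = 2n − 2 and noncentrality d·√(n/2). For n = 70, df = 138 and √(70/2) = √35 = 5.916.

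- d = 0.50: noncentrality 0.50 × 5.916 = 2.958
- d = 0.56: noncentrality 0.56 × 5.916 = 3.313

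The critical value is 1.977 two-sided at .05 and 1.656 one-sided at .05.

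**Step 1: reproduce the plan's figures.**

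| Effect size | Plan states | Two-sided .05, exact t | Two-sided .05, normal approx. | One-sided .05, exact t |
|---|---|---|---|---|
| 0.50 | 90% | 83.6% | 84.1% | 90.3% |
| 0.56 | 95% | 90.8% | 91.2% | 95.1% |

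With the stated two tails, the printed figures are too high by 6.4 and 4.2 percentage points. Using the normal approximation does not explain this. With one side at .05, both figures reproduce.

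**Step 2: is the one-sided match a coincidence?** Smallest n per group by exact t:

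| Target | One-sided .05 | Two-sided .05 |
|---|---|---|
| 90% at d = 0.50 | 70 | 86 |
| 95% at d = 0.56 | 70 | 84 |

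One-sided, 70 is exactly the smallest n for both targets; 69 gives 89.9% and 94.8%. A two-sided alpha of .10 has the same upper critical value and would look the same, but it also contradicts the text.

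**Step 3: what 70 per group can detect two-sided.** 90% power is reached at d = 0.552 and 95% at d = 0.614.

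**Step 4: does the attrition step help?** 140 × 1.15 = 161, or 162 as an even total, which is 81 per arm.

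- No loss at all: 81 per arm gives 88.5% at d = 0.5, still under 90%.
- 15% loss: 162 × 0.85 = 137.7, or 68 to 69 per arm, giving 82.5% to 83.0%.
- Loss at which exactly 140 remain: 1 − 140/162 = 13.6%.

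For reference, 105 per arm would be needed for two-sided 95% power at d = 0.5.

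**The case against.** The strongest reply is that the t-test is only a benchmark. The primary analysis in section 8.3 is a linear mixed model with covariates chosen to raise efficiency, and section 8.2 expects power above the t-test figure. As an illustration, if covariates cut the variance of the change score by a factor 1 − r², an r of about 0.43 would bring two-sided power at d = 0.5 up to 90% with 70 per group.

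Part of this stands. The 84% is the power of the plan's own t-test, and the documents do not determine the power of the mixed model. It does not rescue the printed figures, for three reasons. The plan states no correlation or gain. The mixed-model sentence builds on the t-test figure and does not correct it. And the t-test already compares change scores: with complete data, the baseline-to-post group-by-time contrast in section 8.3 is essentially the same comparison, and covariates entered only as main effects explain level more than change.

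Three smaller points are fair:

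- The software output is not in the document, so the one-sided origin remains an inference.
- Multiplying by 1.15 does what the text says. The count of 68 to 69 per arm treats every lost child as contributing nothing, whereas section 8.3 says that the mixed model uses partial data.
- The error does not affect type I error, randomisation or the analysis model.

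**Conclusion.** The concern holds. Under the test that section 8.2 itself specifies, power with 70 per group is 83.6% at d = 0.5 and 90.8% at d = 0.56. The probability of missing the target effect is therefore 16.4%, not 10%, rising to 17.0% to 17.5% with 69 or 68 completers per arm.

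The result rests on the plan's own inputs: equal groups, a common SD of 2 for change, and two-sided alpha of .05. No outside figure is used. That the stated power does not follow from the stated inputs is certain. That the cause was a one-sided setting is very likely but not documented. Power of about 84% may well be acceptable; the fault is that the plan claims more.

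**What to change.** Check the settings of the saved power calculation, then restate section 8.2 to match the two-sided test. Suggested wording:

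> With 70 evaluable children per group and two-sided alpha of .05, an independent-samples t-test on change has 84% power for an effect size of 0.50. Power reaches 90% at an effect size of about 0.55 (0.552) and 95% at about 0.61 (0.614). Enrolling 162 leaves 70 per group after 13.6% loss. With 15% loss, 68 to 69 children per group complete the study, and t-test power at 0.50 is about 83%, counting completers only.

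If the plan keeps the claim that the mixed model does better, it should state the assumed correlation or covariate strength and the resulting power.

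The cost is a wording change in one section and a less favourable headline figure. No added enrolment is needed. If the investigators do want two-sided 90% power at 0.5 from the t-test, that takes 86 evaluable per group, or 172 in all: 172 × 1.15 = 197.8, so 198 enrolled by the plan's own inflation, or 172/0.85 = 202.4, so 203 if 15% of those enrolled are lost.
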